A randomized controlled trial of the Korean version of the Program for the Education and Enrichment of Relational Skills for Young Adults (PEERS®-YA-K) with autism spectrum disorder

ClinicalTrials.gov identifier: NCT03310775

Study protocol and statistical analysis plan

Update date: 09/06/2020

Recruitment of participants

The participants were recruited from the Child and Adolescent Psychiatric Clinic at Seoul National University Bundang Hospital, through advertisements at the Smile Together Foundation (a local advocacy institute of ASD), a community of child and adolescent psychiatrists, an internet group of families of youth with ASD, and a website for Seongnam Child and Adolescent Psychiatry Mental Health Care Center. Inclusion criteria for young adults included: (1) between 18 and 35 years of age, (2) graduated from high school or expected to graduate by the time the intervention starts, (3) experiencing social difficulties as recognized by young adults and/or social coaches, (4) previously diagnosed with or possibly having a diagnosis of ASD, (5) verbally fluent, (6) full scale intelligence quotient (FSIQ) ≥ 70 by standardized intelligence test, and (7) substantially motivated to participate to intervention. Exclusion criteria included: (1) history of major mental illness (e.g., schizophrenia, bipolar disorder, psychosis, and risk of self-mutilation), (2) significant physical disabilities including visual and/or hearing impairments, (3) clinically significant neurological or physical disease that would preclude participation in group-based social activities, and (4) difficulties for parents to understand and cooperate with the intervention.

The study was approved by IRB of Seoul National University Bundang Hospital (IRB no. B-1611/371-303). Written informed consent was completed by all young adults and social coaches who participated in the present study.

Screening and randomization process

Participants were screened for eligibility by telephone interview using the Phone Screening Interview in the PEERS®-YA treatment manual. Motivation, social problems related to friendships, willingness to follow the rules in the group, comorbidities, and inclusion and exclusion criteria were discussed during the telephone interview.

Diagnosis of ASD was confirmed for screened individuals by two board-certified child psychiatrists based on diagnostic criteria of the fifth edition of the Diagnostic and Statistical Manual of Mental Disorders. The Autism Diagnostic Observation Schedule (ADOS; Lord et al. 2008) and the Autism Diagnostic Interview-Revised (ADI-R; Lord et al. 1994) were used for supporting diagnostic procedures and administered and scored by a special educator trained and certified for these instruments ([name]). IQ was assessed using the Korean Wechsler Adult Intelligence Scale-IV (K-WAIS-IV; Hwang et al. 2012) and assessment of adaptive functioning was conducted using the Korean version of the Vineland Adaptive Behavior Scale-II (K-VABS-II; Volkmar 2013, Hwang, Kim & Hong 2014). Subjects meeting eligibility criteria were randomly assigned to a treatment group (TG) or waitlist control group (CG) using randomized block design. We divided each group into two separate treatment groups of approximately 9–10 young adults.

Subjects

Forty-eight young adults ranging from 18 to 35 years old and their social coaches were recruited for the RCT. Ten participants were excluded during the randomization procedure; six were not adequately motivated, one did not meet the diagnosis of ASD, one had difficulty understanding self-report scales, one had a problem with school, and one had to fulfill a military commitment. A total of 38 participants were screened, but one participant refused to be randomized to the CG. As a result, 37 participants were randomized; 19 were assigned to TG and 18 to CG.

Treatment intervention

The PEERS®-YA consisted of 16 weekly 90-minute sessions. Social coaches and the young adults were given concurrent sessions in separate rooms and each session was led by

five trained treatment leaders. One of the trained treatment leaders ([name]) was a PEERS® Certified Provider for both PEERS® for Adolescents and PEERS®-YA, and another group leader was certified for PEERS® for Adolescents ([name]). Both received 20 hours of comprehensive training through the UCLA PEERS® Clinic by the program developer for each program. The social coach group leaders were board-certified child psychiatrists and special educators with specialty training in the treatment of ASD and group therapy; the young adult group leaders were licensed clinical psychologists and graduate-level trainees in clinical psychology. The behavioral coaches were clinical psychology trainees and psychology graduate students with experience working with children and adolescents with ASD and other developmental disorders. All members of the treatment team were trained and supervised by PEERS® Certified Providers for the duration of the intervention.

The treatment leaders translated the Korean version of the PEERS®-YA Treatment Manual together and had regular meetings (once every week for four months) until the translation was completed. In addition to the treatment sessions, the Social Coaching Handouts and the appendices of the original PEERS®-YA Treatment Manual were translated into Korean, including the Planned Absence Sheet, Phone Roster, In-group Call Assignment log, and Homework Compliance Sheets, the latter of which was used to rate treatment adherence.

After the translation was completed, the PEERS®-YA Certified Provider conducted a 24-hour training workshop on the implementation of the treatment sessions. As part of this training, treatment leaders observed each session of the treatment conducted in Korean by the PEERS®-YA Certified Provider and then established reliability with the treatment protocol before conducting sessions with participants.

The behavioral coaches, who provided support to the group leaders, were fully trained and supervised by a young adult group leader in all content and intervention processes, and attended weekly case conference meetings. Behavioral coaches conducted role-play

demonstrations of targeted skills, provided social coaching with performance feedback during behavioral rehearsal exercises, and monitored treatment fidelity and homework compliance throughout the sessions.

The didactic lessons focused on the social skills necessary for developing and maintaining friendships, romantic relationships, and managing peer conflict and rejection. The lessons included conversational skills, electronic forms of communication, developing friendship networks and finding sources of friends, appropriate use of humor, peer entry and exiting strategies, organizing and having successful get-togethers with friends, handling teasing and chronic bullying in the school or workplace, managing peer pressure, conflict resolution, strategies related to dating etiquette, showing romantic interest, asking someone on a date, going on dates, and general dating guidelines. The detailed processes and characteristics of the PEERS[®]-YA intervention are described by Laugeson (2017).

Within the young adult group, each session included a homework review and didactic lesson including a role-play demonstration of targeted behaviors. Appropriate and inappropriate examples of social etiquette were demonstrated by the behavioral coaches. Didactic lessons were followed by behavioral rehearsal exercises in which young adults practiced the appropriate newly learned skills while receiving performance feedback from the treatment team.

Within the social coach group, homework was reviewed and discussed for two-thirds of the session and homework compliance and quality were recorded. During the review, specific instructions on how to provide assistance and social coaching to the young adults outside of the treatment setting were provided. After homework review and discussion, the social coaches received didactic instruction regarding the targeted social skill being highlighted in the young adult group. Social Coaching Handouts were also distributed, which provided an outline of the rules and steps of the lesson, as well as a summary of upcoming homework

assignments.

The last ten minutes of every 90-minute group included a reunification between young adults and social coaches in which the rules and steps of the targeted skills were highlighted, and homework assignments were given to young adults and social coaches. Research staff monitored treatment fidelity directly from the treatment manual in every session in order to maintain the integrity of the program and ensure that all material was covered.

Measures

Every participant and their social coach in the TG completed outcome measures prior to the start (test 1) and after the completion of the intervention (test 2). Participants and social coaches in the CG completed outcome measures upon entering the study (test 1), prior to the start of treatment (test 2), and after the completion of the treatment (test 3). Four months after completing the program, both groups completed outcome measures to evaluate the maintenance of the treatment effects (TG: test 3; CG: test 4). Assessment schedules for both groups are shown in Figure 1. Social skills training was prohibited for the CG during the waiting period, but medication and general follow-up visits for counseling were allowed.

Primary measures

1. *Autism Diagnostic Observation Schedule, second edition (ADOS-2 Module 4; Lord et al. 2012)*

The ADOS-2 is a standardized test designed to diagnose individuals with ASD by observing their communication and social behaviors during semi-structured play and/or an interview. The ADOS-2 is composed of four modules. Each module is selected according to the expressed language level and chronological age of participants and requires 35 to 40 minutes to administer. The current study used ADOS-2 module 4. Module 4 of the ADOS-2 is

used to diagnose adolescents and adults who are verbally fluent. It is scored on five domains: language and communication, reciprocal social interaction, imagination, stereotyped behaviors, restricted interests, and other abnormal behaviors. In this study, raters on ADOS-2 examined participants blinded to the group of participants and also for pre-treatment or post-treatment.

2. Test of Young Adult Social Skills Knowledge (TYASSK; Laugeson 2017)

The TYASSK is 30-item criterion-based measure developed for use with the PEERS®-YA intervention. The TYASSK is used to evaluate the change in young adults' knowledge of specific social skills taught during the intervention period, with two items derived from each of the lessons. The TYASSK is based on the Test of Adolescent Social Skills Knowledge. The test requires approximately 5 minutes to complete and includes buzzwords related to the didactic lessons. Young adults who participated in this study were asked to select the most fitting of the two possible answers. Scores range from 0 to 30, with higher scores reflecting more knowledge of social skills. The English version of the TYASSK was translated into Korean with the author's permission, and then back-translated into English by a bilingual translator unrelated to this study.

3. Korean Version of the Social Skills Rating System (K-SSRS; Elliott & Gresham 1991, Moon 2003)

The SSRS is a multi-rater feedback questionnaire (teacher, parents, and student forms) to assess social skills, problematic behaviors and academic competence (in the Teacher report form) and it consists of three forms for: pre-school, elementary, and secondary students. The SSRS for secondary students, originally developed for adolescents, has been proven to be appropriate for use in evaluating the social skills of adults with high functioning ASD. It was modified for college students (K-SSRS: college level) and its reliability and utility were

verified by Moon (2003). The K-SSRS consists of 27 items which are rated on a Likert scale from 1 (“not at all”) to 7 (“almost always”).

4. Social Responsiveness Scale-2 (SRS-2; Constantino & Gruber 2012)

The SRS-2 is a 65-item scale used to screen children at risk for ASD and consists of measures regarding the child’s social interactions, communication, and stereotyped behaviors. Individual items are rated on a Likert scale from 1 (“not at all”) to 4 (“almost always”) to measure the severity of ASD symptoms as they occur in natural social settings. The SRS-2 consists of four forms: preschool (ages 2.5-4.5 years), school-age (ages 4-18 years), adult (ages 19 years and older), and an adult self-report. The individual is classified as being at a high risk of ASD when the score is greater than 75. In this study, we used the adult form reported by the caregiver and the self-report form.

Secondary measure

1. Korean version of the Vineland Adaptive Behavior Scale, second edition (K-VABS; Volkmar 2013, Hwang, Kim, & Hong 2014)

The K-VABS is an interviewed survey and measures adaptive behaviors of individuals such as personal and social skills, used for everyday living from birth to age 90. These are based on the reports of primary caregivers and teachers. The K-VABS contains 5 domains each with 2-3 subdomains. The main domains are: Communication, Daily Living Skills, Socialization, Motor Skills, and Maladaptive Behavior (optional). Behaviors are rated on a 0 (a skill that is not used by the individual) – 2 (a skill used most of the time) rating scale. The current study used only the communication, daily living skills, and socialization domains.

2. Beck Depression Inventory (BDI; Beck, Steer, & Garbin 1988, Han et al 1986)

The BDI is a 21-question, self-report inventory, rated from 0 to 3 in terms of intensity. The items are used to assess the intensity of 21 depression-related symptoms and attitudes such as hopelessness and irritability, cognitions such as guilt or feelings of being punished, fatigue, weight loss, and lack of interest in sex. The current study used the BDI-II published in 1996 which was designed for individuals ages 13 and over. The maximum score of the BDI is 63 points, with a suggested interpretation of: minimal range = 0–13, mild depression = 14–19, moderate depression = 20–28, and severe depression = 29–63.

Statistical analyses

Baseline characteristics were compared between the TG and DTG with independent samples t-tests for continuous variables and Fisher's Exact Test for categorical variables. Changes in outcomes between baseline and post-intervention were examined with paired t-tests and also the maintenance of treatment effects in both groups. Post-intervention follow-up measurements were analyzed using repeated measures analysis of variance (ANOVA) comparing both between-group and between-time differences in outcomes with groups by a measured time point interaction. The significance of difference was interpreted with treatment x time interaction from the analysis, and the treatment effect size was assessed with Cohen's d for the interaction (Morris, 2008). All statistical analyses were conducted using SAS version 9.4 (SAS Institute, Cary, NC, USA) and statistical significance was defined as $p < 0.05$.

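### The treatment effect is read from a repeated measures ANOVA interaction with no baseline covariate: valid for tests 1 and 2, but usually less precise than an ANCOVA on the same data

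*Combined protocol and SAP*

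**What the plan says.** The Statistical analyses section gives the model as follows: "Post-intervention follow-up measurements were analyzed using repeated measures analysis of variance (ANOVA) comparing both between-group and between-time differences in outcomes", with a group-by-time interaction. It continues: "The significance of difference was interpreted with treatment x time interaction from the analysis". Cohen's d is taken from the same interaction, and the significance threshold is 0.05. No covariate is named, so the baseline score enters only as one level of the time factor. The section does not say which tests enter the ANOVA.

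The Measures section gives the treatment group (TG) three tests: before the programme, after it, and four months later. The waitlist control group (CG) has four: at entry, before its own treatment, after that treatment, and four months later. Both arms therefore have tests 1 and 2, and CG has been through the programme by its test 3.

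On sample size, the Subjects section states: "37 participants were randomized; 19 were assigned to TG and 18 to CG".

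**The concern.** This is a question of efficiency, not validity. With two tests, the interaction compares mean change between arms, which amounts to subtracting the whole baseline score from each person's post score. When the post score follows the baseline with a slope below 1, full subtraction over-corrects and adds noise. ANCOVA estimates the slope from the data instead.

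In a trial of 37 people, chance baseline differences are not small. What is at stake is a wider confidence interval and lower power than the collected data would allow, and an estimate that moves more with chance imbalance. The plan compares baseline characteristics between arms but states no way to adjust for a difference.

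The unspecified time points bear on this too. The argument applies to the interaction only when the model is restricted to tests 1 and 2. If three common tests entered, the interaction would have (2 − 1)(3 − 1) = 2 degrees of freedom and would mix in the effect of CG's own treatment.

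**Working it through.** The plan states no power, SD or correlation figure, so there is nothing of its own to reproduce.

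**Inputs from the documents:** 19 TG and 18 CG (Subjects); threshold 0.05 (Statistical analyses); tests 1 and 2 taken in both arms (Measures).

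**Assumed:** two-sided testing, no dropout, pre-test SD = 1, post-test SD = L, pre-post correlation r, and a 0.8 SD effect for the power figures.

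**1. Equivalence.** With two tests, the group-by-time F is the square of the two-sample t on change scores. On one simulated data set of 19 and 18, both were 55.23 on 35 degrees of freedom.

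**2. Chance imbalance.** h = 1/19 + 1/18 = 0.1082, so the standard error of the baseline difference is √h = 0.33 SD. Given an observed imbalance of that size and L = 1, the change-score and adjusted estimates differ by (1 − r) × 0.329: 0.16, 0.13 and 0.10 SD at r = 0.5, 0.6 and 0.7.

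**3. Variances.**
- Change score: (1 + L² − 2rL)h
- ANCOVA: L²(1 − r²)h × k, where k = 1 + 1/(37 − 4) = 1.030 is the cost of estimating the slope
- At L = 1 the ratio ANCOVA/change is k(1 + r)/2. For r = 0.5 this is 1.030 × 0.75 = 0.77.
- Equivalent sample size is 37/ratio. For r = 0.5 this is 37/0.773 = 48.

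**4. Results at L = 1.** Half-width is the t quantile times the true standard error, with 35 df for change and 34 for ANCOVA. Power is from the noncentral t. Pairs are change score, then ANCOVA.

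| r | Variance ratio | Equivalent N | 95% CI half-width (SD) | Power, 0.8 SD effect |
|---|---|---|---|---|
| 0.3 | 0.67 | 55 | 0.790, 0.647 | 52%, 68% |
| 0.5 | 0.77 | 48 | 0.668, 0.588 | 66%, 77% |
| 0.6 | 0.82 | 45 | 0.597, 0.543 | 75%, 83% |
| 0.7 | 0.88 | 42 | 0.517, 0.485 | 86%, 90% |
| 0.9 | 0.98 | 38 | 0.299, 0.296 | both above 99% |

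**5. Where the gain stops.**
- At L = 1, break-even is r = 2/k − 1 = 0.94.
- At L = 1.2 the ratio is 0.90, 0.95, 0.996 and 1.03 at r = 0.5, 0.6, 0.7 and 0.8. As L rises above 1, the gain first disappears at L of about 1.54, 1.35, 1.21 and 1.11 for those r.
- At L = 0.8 and r = 0.7 the gain is larger (ratio 0.65).
- Apart from k, the change-score variance exceeds the ANCOVA variance by (1 − rL)²h, which cannot be negative. The ratio therefore never exceeds k: ANCOVA loses at most about 3% of variance.

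**6. Simulation (40,000 trials per setting, 19 versus 18).** Under the null, type I error stayed close to 0.05 for both methods and neither showed bias. With a true effect of 0.8, both averaged 0.80. Simulated variance ratios matched the formula.

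**The case against.** The planned analysis contains no error. The interaction test is valid, its effect size is matched to it, and nothing in the documents requires baseline adjustment. That stands, and it is why this is a recommended improvement rather than a correction.

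The size of the gain rests on figures that the documents do not give. It is modest in plausible settings: for an assumed 0.5 SD effect, power is 48% versus 53% at r = 0.7 and 91% versus 92% at r = 0.9. With L = 1.2 and r = 0.7 the half-widths are practically equal (0.582 and 0.581 SD), and at r = 0.8 ANCOVA is slightly wider (0.489 against 0.482). This also stands. No material loss has been shown for any particular measure in this trial.

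The document is in the past tense and carries a 2020 update date. If results are already known, an ANCOVA cannot become the deciding analysis, so the power figures describe what was available at planning and not what a late addition delivers. A late addition delivers a supplementary, usually narrower interval, at the price of a second p-value for each outcome.

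The unspecified time points are a separate gap, and could be closed while keeping the interaction. That is also true. But the objection leaves the main point in place: ANCOVA uses the same data, its loss is capped at about 3% of variance, and its possible gain is considerably larger.

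**Conclusion.** The concern holds as an efficiency point. For tests 1 and 2 the planned interaction is valid and unbiased, and usually less precise than ANCOVA. With equal SDs and no dropout, the variance saving runs from about 33% at r = 0.3, through 23% at 0.5 and 12% at 0.7, to 2% at 0.9, and is gone above about 0.94. A larger post-test SD can shrink or slightly reverse it; a smaller one increases it. The actual size is unknown because r and the SDs are not given, and it may differ between the observer-rated, self-report, caregiver and knowledge measures. The change is worth making but is not essential to the validity of the trial.

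**What to change.** For each outcome, fit test 2 score = group + test 1 score and report the adjusted TG minus CG difference with its 95% CI and p-value. State that only tests 1 and 2 enter the randomised comparison, and treat later tests as evidence on maintenance. Keep the planned interaction result and its Cohen's d alongside. If results were known when the ANCOVA was added, label it as such, do not let it replace the planned result, and report both even where they disagree.

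The cost is one model statement and one degree of freedom per outcome, with no new data.

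### The between-group significance test is not tied to tests 1 and 2, the only randomised comparison of treated with untreated participants

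*Combined protocol and SAP*

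**What the plan says.** The Subjects section reports that "37 participants were randomized; 19 were assigned to TG and 18 to CG".

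The Measures section sets the schedule. For TG: "Every participant and their social coach in the TG completed outcome measures prior to the start (test 1"), with test 2 once the intervention is over. For CG: "Participants and social coaches in the CG completed outcome measures upon entering the study (test 1), prior to the start of treatment (test 2"); its test 3 follows CG's own course. A last assessment, four months after each group finishes, is made "to evaluate the maintenance of the treatment effects (TG: test 3; CG: test 4"). TG therefore has three tests and CG four.

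The Statistical analyses section examines change from baseline to post-intervention, and maintenance in both groups, with paired t-tests, which are within-group. The between-group model comes next: "Post-intervention follow-up measurements were analyzed using repeated measures analysis of variance (ANOVA"), with a group by time-point interaction. Inference rests on that one term: "The significance of difference was interpreted with treatment x time interaction from the analysis". The size of the effect is tied to the same term, in that "the treatment effect size was assessed with Cohen's d for the interaction". Significance is p < 0.05 and the software is SAS 9.4. The section does not list the tests in the model, define an analysis set, give a rule for a missing test, or name a SAS procedure.

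**The concern.** The only between-group inference is the interaction from the ANOVA, and the measurements assigned to that ANOVA are described as follow-up measurements. The step from baseline to post-intervention is explicitly assigned only to paired t-tests. Taken literally, the single between-group test can include an assessment at which CG has already been treated.

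The wording leaves three analyses open:

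- tests 1 and 2 only;
- tests 1 to 3 matched by number (a standard ANOVA cannot use test 4, which TG lacks);
- tests matched by phase, with TG test 3 set against CG test 4, when both groups have been treated.

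These answer different questions. With later tests in, a significant interaction could arise from what happens after CG's treatment, and it would not by itself be evidence that treatment beats waiting. The second and third analyses also make inclusion in the randomised comparison depend on attending later tests, if incomplete cases are deleted.

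**Working it through.** **Figures in the plan.** There is no power calculation, SD, effect size or attrition rate to reproduce. The participant flow agrees: 48 − 10 − 1 = 37 = 19 + 18.

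**Treatment status at each test (Measures section).**

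| Test | TG | CG |
|---|---|---|
| 1 | untreated | untreated |
| 2 | treated | untreated |
| 3 | four months after treatment | treated |
| 4 | none | four months after treatment |

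Only the step from test 1 to test 2 sets treated against untreated.

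**Inputs.** From the documents: 19 and 18 participants, and alpha 0.05 (taken as two-sided). Assumed: the change from test 1 to test 2 has SD 1, and correlation between tests is equal, so the within-person error variance is 0.5. The group gaps and all loss rates below are also assumed.

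**Benchmark, tests 1 and 2.** The noncentrality is (19 × 18 / 37) × d² = 9.243 × d². With d = 0.948 this is 8.31. On F(1, 35), power is 80.0%.

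**Tests 1 to 3, complete data.** The noncentrality is 9.243 × Σ(gap − mean gap)² / 0.5, on F(2, 70).

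| Group gap at tests 1, 2, 3 (SD) | Σ(gap − mean)² | Noncentrality | Interaction significant, tests 1–3 | Tests 1–2 |
|---|---|---|---|---|
| 0, 0, 0.948 | 0.599 | 11.08 | 83.9% | 5% |
| 0, 0.948, 0.474 | 0.449 | 8.31 | 71.5% | 80.0% |
| 0, 0.948, 0 or 0, 0.948, 0.948 | 0.599 | 11.08 | 83.9% | 80.0% |

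Simulation (20,000 runs, correlation 0.5 and 0.7) gives 84.1% and 84.5% for the first row, with 4.8% and 5.0% for tests 1–2. It gives 71.5% and 72.2% for the second row.

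The first row is the main result: nothing happens in the randomised contrast, yet the test is usually significant. The third row shows that later tests do not always cost power. The problem is what is being tested.

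**Conditional part: people lost.** Let q be the loss at each post-baseline test, with incomplete cases deleted.

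| q | Kept, tests 1–2: 37(1 − q) | Kept, tests 1–3: 37(1 − q)² | Had tests 1 and 2 but dropped: 37(1 − q)q |
|---|---|---|---|
| 5% | 35.2 | 33.4 | 1.8 |
| 10% | 33.3 | 30.0 | 3.3 |
| 15% | 31.5 | 26.7 | 4.7 |

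**Conditional part: bias.** Let the change from test 1 to test 2 be N(0.5, 1) in TG and N(0, 1) in CG, with both tests complete. Loss at test 3 is logistic in that change, with slope 0.7 or 1.0 per SD poorer (odds ratio 2.0 or 2.7). Bias is the difference in mean change among those kept, minus 0.5.

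| Dependence | Slope | Bias at 5% loss | Bias at 10% loss |
|---|---|---|---|
| TG only (loss set at TG's mean change) | 0.7 | +0.041 | +0.078 |
| TG only | 1.0 | +0.067 | +0.119 |
| Both arms, one curve (loss set at zero change) | 0.7 | −0.011 | −0.020 |
| Both arms, one curve | 1.0 | −0.023 | −0.037 |

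Using all test 1 and 2 data, simulated bias is at most 0.005 SD.

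**The case against.** The best defence is that the plan already means tests 1 and 2. Maintenance has its own within-group paired t-tests, and a single Cohen's d for the interaction fits a two-time-point model better than one with three. If that is what was done, no later test enters and none of the harm arises. This makes the benign reading plausible. It does not settle the matter, because the same section assigns follow-up measurements to the ANOVA. The assessment-schedule figure cited under Measures was not available for this check and may bear on how tests were aligned.

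The second defence is that no attrition is shown. The Measures section says that participants completed the measures, no loss after randomisation is reported, and no SAS procedure is named, so deletion of incomplete cases is an inference from what a standard repeated measures ANOVA does. This stands. A reader might infer that participants were in fact dropped or that the result is biased; the documents support neither. The completion wording describes the schedule and gives no counts per test, so it does not rule out loss either.

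A reader might also take the power of a two-group t-test on the reduced numbers as the power of the three-test ANOVA. It is not, because that interaction has two degrees of freedom and its power depends on the gap at test 3. Nor should the person who refused randomisation to CG be read as a post-randomisation exclusion: the Subjects section places that refusal before the 37 were allocated.

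**Conclusion.** The concern holds as a gap in specification. The section does not fix the contrast on which its only between-group inference rests, and one natural reading of its words brings in a test at which CG has been treated. Under that reading the interaction does not test the randomised comparison even with no missing data: about 84% significant against 5% in the assumed late-gap scenario, and about 72% power against 80% if the effect halves. These sizes rest on assumed gaps and equal correlation between tests.

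The missing-data harm is secondary and needs three things together: later tests in the model, someone missing one, and deletion of incomplete cases. At an assumed 10% loss per test it removes about 3 of 37 people whose tests 1 and 2 are complete. Bias would be +0.04 to +0.12 SD if loss depends on response in TG only, and −0.01 to −0.04 SD if in both arms. If only tests 1 and 2 enter, none of this harm arises. If later tests enter but nobody missed one, the loss and bias vanish and the wrong-contrast problem remains.

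**What to change.** State that the primary between-group analysis is the group difference in change from test 1 to test 2, in all 37 randomised participants as allocated. Estimate it with a likelihood-based mixed model (group, time, group by time) that keeps everyone with any assessment, and take significance from that single contrast and not from an overall interaction across later tests. The minimum alternative is an ANOVA limited to tests 1 and 2, which removes the later-test problem but still drops anyone missing test 2.

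Analyse later tests only as within-group contrasts: TG test 3 against test 2 for maintenance, CG test 3 against test 2 for its own treatment, and CG test 4 against test 3 for maintenance. Report the number assessed per arm at each test.

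The cost is a few sentences and a run in the SAS version already named, on data already scheduled, with no new participants or visits. The downsides are slightly more analysis work and a missing-at-random assumption. The precision gain of the mixed model over a tests 1–2 ANOVA is small: with an assumed 10% loss at each of tests 2 and 3, simulated SEs were 0.343–0.351 against 0.347–0.352 SD. The main benefit is fixing the contrast.
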